ANNEX 11. SUMMARY OF PRODUCT CHARACTERISTICS FOR SUTENT, VOTRIENT, NEXAVAR	

1. LIST OF ABBREVIATIONS

Abbreviation	Definition	
AE	Adverse Event	
AEM	Adverse event monitoring	
AEMPS	Agencia Española de Medicamentos y Productos Sanitarios (Spanish Agency of Medicines and Medical Devices)	
AR	Autonomous Regions	
AUC	Area Under the Curve	
CR	Complete Response	
CRF	Case Report Form	
CTCAE version 4	Common Terminology Criteria (Common Terminology Criteria for Adverse Events, version 4) of the U.S. Department of Health and Human Services	
CVA	Cerebrovascular Accident	
DMP	Data management plan	
DOR	Duration of response	
DP	Disease Progression	
ECOG	Eastern Cooperative Oncology Group. Scale to measure the quality of life of oncology patients with scores running from 0 to 5	
eCRF	Electronic Case Report Form	
EDP	Exposure during pregnancy	
FDA	Food & Drug Administration	
GCP	Good Clinical Practice	
HFS	Hand-Foot Syndrome	
IC	Informed Consent	

-		
ICH	International Conference on Harmonisation	
IEC	Independent Ethics Committee	
mRCC	Metastatic Renal Cell Carcinoma	
NIS	Non-interventional study	
ORR	Objective Response Rate	
OS	Overall Survival	
PFS	Progression-Free Survival	
PR	Partial Response	
RCC	Renal cell carcinoma	
SAE	Serious Adverse Event	
SAE	Serious Adverse Event	
SD	Stable Disease	
SRSD	Single reference safety document	
ТКІ	Tyrosine kinase inhibitor	
TT	Treatment Time	
TTF	Time to Treatment Failure	

3. ABSTRACT

Prospective, multicentre, observational study in patients with metastatic renal cell carcinoma (mRCC) receiving a tyrosine kinase inhibitor as first-line treatment according to routine clinical practice, designed to evaluate the incidence of fatigue and hand-foot syndrome in order to determine how these affect the baseline characteristics of the patient and his/her disease (age, gender, baseline status, tumour histology, etc.) and the patient's lifestyle as such side effects develop.

[figure not shown]
STUDY TITLE

Prospective, multicentre, observational study on fatigue- and hand-foot syndrome-related quality of life in patients with metastatic renal cell carcinoma receiving a tyrosine kinase inhibitor as first-line treatment (TROYA Study)

PROTOCOL CODE: A6181218 (PFI-ITK-2015-01) TROYA

COORDINATING INVESTIGATOR:

The scientific coordinator will be responsible for maintaining the methodological rigour of the study, both in the design phase and in the evaluation of results and writing of the final report. He will guarantee the ethical conduct of the study, maintaining scientific support for all participating doctors until the results are published.

STUDY SITES:

It is initially considered optimal to include patients at approximately 35 Spanish sites (see ANNEX 7 to the protocol, which contains the list of proposed sites).

IEC THAT WILL ASSESS THE STUDY

IEC of Navarre

Secretary of the Independent Ethics Committee of Navarre (IEC) [name]

[contact] [contact] Email: [contact]

STUDY OBJECTIVES

PRIMARY OBJECTIVE

Fatigue-related quality of life of patients receiving a tyrosine kinase inhibitor evaluated using the validated 13-item FACIT-Fatigue scale for patients with metastatic renal cancer in Spanish.^{1,2}

SECONDARY OBJECTIVES

- 1) Quality of life in patients with palmar-plantar erythrodysaesthesia (hand-foot syndrome).
- 2) To assess the following adverse effects according to version 4 of the CTCAE (Common Terminology Criteria for Adverse Events): any grade of fatigue and hand-foot syndrome (HFS).
- 3) To study what role aerobic exercise (walking quickly, running, swimming, playing tennis, dancing and/or riding a bike) plays in the onset of fatigue before starting and during treatment.
- 4) To evaluate what impact the time of drug administration, napping, off-treatment periods, temporary treatment breaks and dose reductions have on controlling fatigue and hand-foot syndrome.
- 5) Time to Treatment Failure (TTF), defined as the time from the start of treatment with a tyrosine kinase inhibitor to tumour progression, treatment discontinuation for any reason or death from any cause.
- 6) Progression-Free Survival (PFS) (median): time from the start of treatment with a tyrosine kinase inhibitor to tumour progression or death from any cause.
- 7) Objective Response Rate according to RECIST version 1.1.

DESIGN

Prospective, multicentre, observational, post-authorisation study in patients aged ≥ 18 years diagnosed with metastatic renal cell carcinoma who are to be given a tyrosine kinase inhibitor as first-line treatment.

This is a non-interventional study and therefore the decision to prescribe any treatment will be made prior to and independently of the patient's participation in the study; i.e. patients will receive the same medication whether they participate in the study or not according to the clinical judgement and normal clinical practice of the doctor responsible for the patient. Moreover, no additional tests are to be performed as part of the study.

STUDY CONDITION

Metastatic renal cell carcinoma.

STUDY POPULATION AND TOTAL NUMBER OF SUBJECTS

A population of 100 patients aged 18 years or over and diagnosed with metastatic renal cell carcinoma who are to start first-line treatment with a tyrosine kinase inhibitor according to routine clinical practice is to be studied at 35 Spanish sites.

INCLUSION AND EXCLUSION CRITERIA

3.1.1. Inclusion Criteria

The patients must meet all the inclusion criteria to participate in the study:

1) Patients \geq 18 years old and diagnosed with metastatic RCC who, in the investigator's opinion, are candidates for starting first-line treatment with a tyrosine kinase inhibitor according to routine clinical practice.

2) Patients who have no contraindications to the treatment.

3) Baseline ECOG ≤ 2 .

4) Patients who are able to give informed consent on their own without the need for a legal representative.

5) Committed patients who are able to complete the quality of life questionnaires and patient diary on their own without the need for a legal representative.

3.1.2. Exclusion Criteria

Patients must not meet any of the exclusion criteria described below.

1) Patients who are not candidates for first-line treatment with a tyrosine kinase inhibitor.

2) Patients who are receiving the treatment as second-line or subsequent therapy.

3) Untreated hypothyroidism.

4) Untreated severe anaemia.

5) Pregnancy or breast-feeding.

6) Myocardial infarction or cerebrovascular accidents (CVA) within the last 6 months.

7) Severe hepatic impairment.

8) Concomitant use of potent inhibitors or inducers that interact with hepatic cytochrome CYP3A4.

QUALITY OF LIFE:

 Fatigue-related quality of life of patients evaluated using the validated 13-item FACIT-Fatigue scale for patients with kidney cancer in Spanish. Company FACIT.ORG (USA) (ANNEX 8). Quality of life in patients with palmar-plantar erythrodysaesthesia (hand-foot syndrome). To be evaluated according to CTCAE Version 4.0 Published: May 28, 2009 (v4.03: June 14, 2010) with scores running from 1 to 3 (see ANNEX 9).

SCHEDULE

Date of submission to AEMPS for classification: October 2015

Proposed date of submission to the IEC: November 2015

Proposed date of inclusion of the first patient in the study: February 2016

Proposed end-of-recruitment date: August 2017 or after recruiting 100 patients, whichever occurs first.

Recruitment period: 18 months.

Proposed date of the end of data collection: May 2018 or whenever the last patient passes to the 2nd line of treatment, whichever occurs first.

Expected date of Interim study report: After completing the 9 months of fatigue-related quality of life follow-up in all patients, estimated July 2018.

Expected date of Final study report: October 2018

SOURCE OF FUNDING

Pfizer SLU, as sponsor of the study, will provide financial compensation to the participating sites/investigators. Such compensation will be explicit and transparent, without prejudice to the internal rules of their employing agencies and in accordance with specific regulations in the ARs and at the sites where the study is conducted.

Fees are to fund the collection and transcription of clinical and epidemiological data from patients and the quality of life questionnaires to the case report forms.

AMENDMENTS AND UPDATES

None

Amendment No.	Date	Substantial or administrative amendment	Amended protocol section(s)	Summary of change(s)	Reason

4. MILESTONES

Milestone	Proposed date
Start of data collection	
Proposed date of the first patient's first visit, FSFV	February 2016
End of data collection	
Proposed date of the last patient's last visit, LSLV	May 2018
Interim study report	
Proposed date of drafting (or remittance) of Interim report	July 2018
Final study report	
Proposed date of drafting (or remittance) of Final report	October 2018

5. STUDY RATIONALE

BACKGROUND

Over recent years, a better understanding of the molecular biology of renal cell cancer (RCC) has led to an unprecedented development of therapies for this disease. As a result, various targeted agents have been approved and used for the management of RCC that have led to an improvement in both the progression-free survival (PFS) and overall survival (OS) of patients diagnosed with this disease.³

Among these new agents, sunitinib, pazopanib and sorafenib are drugs that are recommended in all guidelines for the first-line treatment of RCC. Sunitinib is the targeted agent most widely used in routine clinical practice today. Sunitinib and sorafenib are oral tyrosine kinase inhibitors that inhibit vascular endothelial growth factor receptors (VEGFR-1, VEGFR-2 and VEGFR-3), platelet-derived growth factor receptors (PDGFR), c-Kit, RET and FLT3. Pazopanib is an oral tyrosine kinase receptor inhibitor that inhibits vascular endothelial growth factor receptors, platelet-derived growth factor receptors (PDGFR) and c-Kit.

Sunitinib has been approved for the management of patients diagnosed with metastatic RCC (mRCC) based on the results of the randomised, controlled, double-blind, phase III study⁴ comparing sunitinib with interferon alpha as first-line treatment for 750 patients with mRCC. The study showed significant improvement in the efficacy of sunitinib compared with interferon with a median PFS (primary endpoint of the study) of 11 months vs. 5 months (p < 0.001) for the sunitinib and interferon arms, respectively.

Pazopanib has been approved for patients diagnosed with mRCC based on data from a randomised, multicentre, double-blind, placebo-controlled study that included 435 patients with advanced and/or metastatic RCC who had not received previous treatment, or who had received first-line treatment with IL-2 or interferon alpha. PFS was 9.2 months for the pazopanib group versus 4.2 months for the placebo group (< 0.0000001).¹⁰

Sorafenib was initially approved for the treatment of mRCC in patients with advanced renal cell carcinoma in whom previous therapy with interferon alpha or interleukin-2 had failed or who were considered unsuitable for such therapy based on the results of a randomised, multicentre, double-blind, placebo-controlled, phase III trial involving 903 patients. The median PFS was 167 days in patients randomised to sorafenib compared to 84 days in patients receiving placebo (p < 0.000001). Currently, as a result of the approval of new drugs for the treatment of mRCC, its use in the first-line setting (approval for patients who are not candidates for cytokine therapy) is not very common and it is more habitually used as second-line or subsequent therapy.¹¹

With most drugs used for the treatment of mRCC, data indicate the importance of maintaining dose intensity, since it is correlated with response and survival. This is shown, for example, in a meta-analysis of 6 studies including a total of 443 patients with pharmacokinetic data diagnosed with mRCC and treated with sunitinib. This meta-analysis demonstrated that increased exposure

to sunitinib, reflected by a greater area under the curve (AUC), was associated with improved PFS, improved OS and a higher response rate.⁵ A relationship has also been found between exposure to pazopanib and efficacy.⁶

In the pivotal phase III clinical trial involving sunitinib, 19% of patients discontinued treatment due to side effects and 38% of patients had to temporarily interrupt treatment, while 50% of patients had to reduce the standard dose in order to control adverse effects.^{7,8} In fact, temporary dose interruptions are one strategy contemplated in the summary of product characteristics for this medicinal product.

The most common grade 3-4 toxicity was hypertension (12%), followed by fatigue (11%), diarrhoea (9%) and HFS (9%).^{4,7}

In the sunitinib expanded access programme, 8% of patients discontinued treatment due to serious adverse effects while 30% required dose reductions due to toxicity.⁹

Pazopanib: 19% of cytokine-pretreated patients discontinued treatment versus 12% of treatmentnaive patients.¹⁰

10% of patients being treated with sorafenib stopped treatment due to side effects in the pivotal trial. 11

Although the therapeutic goal in the treatment of metastatic renal cell carcinoma is to prolong the survival of patients, it is equally important to keep treatment-related toxicities as low as possible in order to achieve patient adherence to treatment, thereby maximising dose intensity, which is the determining factor for obtaining better results in the long term. The high incidence of dose reduction and treatment interruptions due to adverse effects could lead to decreased plasma drug exposure and reduced clinical benefit.^{5,6} The drug's tolerability may be a barrier when it comes to maximising the potential efficacy of therapy.

Therefore, maintaining the dose is a challenge, with side effects such as fatigue, diarrhoea, hand-foot syndrome or hypertension. In fact, fatigue and diarrhoea are the most worrying symptoms when questioning patients,¹² to such an extent that 50-75% of patients receiving treatment complains about some degree of asthenia, although only 7-11% of cases interfere with the activities of daily living.

In studies, TKI-related fatigue is highly variable in both degree and duration, although it is generally mild to moderate.¹³ In the case of sunitinib, this is especially significant since this is a drug that is administered intermittently. Fatigue typically occurs 2-3 weeks after the start of treatment, increases in intensity during weeks 3 and 4, and tends to improve during the 2-week off-treatment period, during which patients are comparatively better than during on-treatment weeks. This has resulted in the use of alternate sunitinib scheduling in clinical practice in order to improve tolerability and maintain effective dose intensity, with the schedule of 14 days on and 7 days off being the most commonly used (2/1 schedule). Results based on the use of these schedules by different groups have recently been published (retrospective analyses).^{14,15} The European Association of Urology Guidelines¹⁶ on Renal Cell Carcinoma 2015 describe the

schedule of 2 weeks on and 1 week off treatment for the management of toxicity in patients being treated with sunitinib.

It is not clear what percentage of fatigue is cancer-related and what percentage is attributable to the tyrosine kinase inhibitor as both types of fatigue are very similar and often coexist. The mechanisms of fatigue are not well described. Changes at muscle level can cause peripheral fatigue, whereas central nervous system failure to activate the motor neurons adequately would cause central fatigue.

Fatigue is more common in men, particularly in young men, resulting in repeated treatment interruptions. However, fatigue tends to decrease with increasing treatment cycles. Whether this phenomenon represents an adaptation and/or learning by the patient or a true lower incidence is unknown.

It is important to rule out other causes that may cause or exacerbate fatigue, such as dehydration, hypothyroidism, hypercalcaemia, anaemia or depression. These adverse effects must be monitored every 2-3 cycles.¹³

In the phase I study published by Faivre,¹⁷ asthenia was associated with an increase in daytime napping and night-time somnolence. Age and baseline status (ECOG) at the start of the study did not predict asthenia.

Patient education is crucial. It is necessary to explain that this adverse effect will quite probably appear and we have strategies to manage it if it occurs.

It is interesting to see fatigue in the context of the disease and to readjust the patient's expectations, explaining that it will be necessary to adapt his/her everyday activities to save energy.¹³

Some authors recommend training with aerobic exercises for 30 minutes 3 times a week. Randomised clinical trials have demonstrated better responses in oncology patients using resistance training. It is important to take into account the patients' previous level of activity and cardiac output before recommending exercise.

RATIONALE FOR THIS STUDY

In view of the above, we believe it is appropriate to initiate a study to prospectively assess fatigue-related quality of life in patients with mRCC who are starting treatment with a tyrosine kinase inhibitor.

The patients' quality of life will be evaluated using the FACIT-Fatigue questionnaire and a Patient Diary (both to be completed by the patient) every 6 weeks.

To our knowledge, no fatigue-related quality of life studies in European patients with this condition have been published to date.

6. OBJECTIVES

PRIMARY OBJECTIVE

Fatigue-related quality of life of patients receiving a tyrosine kinase inhibitor evaluated using the validated 13-item FACIT-Fatigue scale for patients with metastatic renal cancer in Spanish.^{1,2}

SECONDARY OBJECTIVES

- 1) Quality of life in patients with palmar-plantar erythrodysaesthesia (hand-foot syndrome).
- 2) To assess the following adverse effects according to version 4 of the CTCAE (Common Terminology Criteria for Adverse Events): any grade of fatigue and HFS.
- 3) To study what role aerobic exercise (walking quickly, running, swimming, playing tennis, dancing and/or riding a bike) plays in the onset of fatigue before starting and during treatment.
- 4) To evaluate what impact the time of drug administration, napping, off-treatment periods, temporary treatment breaks and dose reductions have on controlling fatigue and hand-foot syndrome.
- 5) Time to Treatment Failure (TTF), defined as the time from the start of treatment with a tyrosine kinase inhibitor to tumour progression, treatment discontinuation for any reason or death from any cause.
- 6) Progression-Free Survival (PFS) (median): time from the start of treatment with a tyrosine kinase inhibitor to tumour progression or death from any cause.
- 7) Objective Response Rate according to RECIST version 1.1.

7. METHODS OF INVESTIGATION

7.1. Study design

Prospective, multicentre, observational, post-authorisation study in patients aged ≥ 18 years diagnosed with metastatic renal cell carcinoma who are to be given a tyrosine kinase inhibitor as first-line treatment.

The study will evaluate measures to improve patients' quality of life, such as time of drug administration, napping, temporary treatment breaks and dose reductions.

Fatigue-related quality of life will be evaluated using the Spanish version of the *FACIT*–Fatigue **Questionnaire**, which will be completed by the patient individually after having been explained by the clinician or a person appointed by the investigator (nursing staff, clinical trial coordinator)

in the treatment room or another room during the scheduled visits, once the patient understands how to complete the form.

The FACIT–Fatigue questionnaire will be handed out together with the patient diary at the following treatment times, which coincide with the visits, according to the department's protocol:

- 1) **Baseline** (before starting the treatment)
- 2) Month 3
- 3) Month 6
- 4) Month 9 or upon treatment discontinuation
- 5) Additional visits according to the oncology department's clinical practice: additional visits may be recorded on the case report form (e.g. at 15 days)

The patient will also complete this FACIT-Fatigue questionnaire at home **at the start of each cycle** (for sorafenib and pazopanib a cycle will be 6 weeks of treatment), even if this does not coincide with scheduled visits to the hospital.

The hand-foot syndrome-related quality of life evaluation that patients may be asked to take part in will be performed on the basis of the CTCAE V4.03 2010 with scores running from 1 to 3 (see ANNEX 9).

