## • Has taken the medication:

- In the morning (between 7 am and 12 noon)
- In the afternoon (between 1 pm and 7 pm)
- At night (between 8 pm and 6 am)
- I have not taken any medication this week

For each one of the weekly habits described above, a summary calculation will be made (after three months) of each patient's habits in terms of daytime rest, physical exercise and taking their medication, taking the options marked with greater frequency in the last 12 weeks into account.

FACIT\_Fatigue: The main measures of centrality and dispersion measures will be calculated (mean, standard deviation, median, minimum, maximum, IR and 95%CI ) from the score obtained in the FACIT\_Fatigue quality of life scale, calculated as described in ANNEX 1. The absolute and relative frequency of patients with severe fatigue, being those with a score of less than 30 points on the FACIT\_Fatigue scale, will also be presented.

For each one of the evolution visits (week 6, week 12, week 18, week 24, week 30 and week 36), a study will be performed to ascertain whether significant changes have occurred in fatigue-related quality of life versus the previous evaluation, and defined as:

- **Improvement:** if there is an increase of more than 4 points in the FACIT\_Fatigue scale score versus the previous evaluation
- **Maintenance:** if the score on the quality of life scale does not vary by more than 4 points versus the previous evaluation
- **Worsening:** if the score obtained on the Facit\_Fatigue scale decreases by more than four points versus the previous evaluation.

Significant associations will be sought between the habits of daytime rest, the practice of physical aerobic exercise, medication taken, dose and treatment schedule changes, dose interruptions and the number of days of treatment

interruption depending on the evolution in the evaluation of the fatigue in the FACIT\_Fatigue over the last six weeks. The Pearson chi-squared test will be used for this purpose (or Fisher's exact test for 2x2 tables or likelihood ratio test for mxn tables, if necessary).

- Treatment: For each one of the treatment cycles received by patients during the 9-month follow-up, the following will be studied:
  - **Dose change:** the absolute and relative frequency of patients who have changed doses since the last cycle will be provided. In the sub-population of patients with dose changes in the last cycle, their frequency distribution will be presented according to:

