    - Number of dose changes received
      - 1 change \_ New dose
        - Sunitinib 50 mg 4/2 regimen
        - Sunitinib 50 mg 2/1 regimen
        - Sunitinib 37.5 mg 4/2 regimen
        - Sunitinib 37.5 mg 2/1 regimen
        - Sunitinib 25 mg 4/2 regimen
        - Sunitinib 25 mg 2/1 regimen
        - Pazopanib 800 mg/24 hours continuous
        - Pazopanib 400 mg/24 hours continuous
        - Sorafenib 400 mg/24 hours continuous
        - Sorafenib 400 mg/12 hours continuous
      - 2 changes\_ New dose
        - Sunitinib 50 mg 4/2 regimen
        - Sunitinib 50 mg 2/1 regimen
        - Sunitinib 37.5 mg 4/2 regimen
        - Sunitinib 37.5 mg 2/1 regimen
        - Sunitinib 25 mg 4/2 regimen
        - Sunitinib 25 mg 2/1 regimen
        - Pazopanib 800 mg/24 hours continuous
        - Pazopanib 400 mg/24 hours continuous
        - Sorafenib 400 mg/24 hours continuous
        - Sorafenib 400 mg/12 hours continuous
  - **Treatment interruptions:** the absolute and relative frequency of patients who have interrupted the treatment since the last cycle will be given. In

the sub-population of patients with treatment interruptions, their frequency distribution will be presented according to:

- Number of treatment interruptions
  - 1
  - 2
  - 3
  - 4 •
  - 5 •
  - ...
- Total calculation of days of treatment interruption
  - <7 days
  - 7-14 days
  - >14 days

In order to study the evolution of patients in terms of the presence of AEs (HFS and fatigue), patient habits in terms of daytime rest, aerobic physical exercise and taking medication, paired data comparisons will be performed between each one of the visits with the results of the previous visit, as well as of each one of the visits with regard to the results presented at the baseline visit, using, for this purpose, the non-parametric sign tests for categorical variables or the McNemar test in the case of dichotomous variables. In order to ascertain whether there is a significant evolution in the score obtained on the FACIT Fatigue scale throughout the study, comparisons of paired data will be performed for each one of the assessments with regard to the baseline value and with regard to the

previous evaluation using the Student t-test for paired data or the non-parametric Wilcoxon test, as appropriate.

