#### 9 LIST OF TABLES AND TABLE OF CONTENTS

Table/Graph number			Table/Graph title					
1.			Included and evaluable population					
2.			Descriptive analysis					
	.1		Demographic and disease information					
		.1	Age					
		.2	Time from diagnosis and from the advanced diagnosis of the disease					
		.3	Gender					
		.4	ECOG at time of diagnosis, Heng prognostic criteria and site of metastasis					
		.5	Histological type					
		.6	Smoking					
	.2		Dosage and treatment regimen of tyrosine kinase with which the patient begins treatment					
3.			Analysis of evolution					
	.1		Presence of palmar-plantar erythrodysesthesia of any grade (month 3, month 6, month 9)					
		.1	Association between medication intake habits and evolution of hand- foot syndrome (every three months)					
		.2	Association between dose changes and evolution of hand-foot syndrome (every three months)					
		.3	Association between dose, treatment regimen received and the evolution of hand-foot syndrome (every three months)					
		.4	Association between temporary treatment interruptions and evolution of hand-foot syndrome (every three months)					
	.2		Presence of fatigue of any grade (baseline, month 3, month 6, month 9)					
		.1	Association between daytime rest habit and fatigue evolution (every three months)					
		.2	Association between daytime physical exercise and fatigue evolution (every three months)					
		.3	Association between daytime medication-taking habits and fatigue evolution (every three months)					
		.4	Association between daytime dose changes and fatigue evolution (every three months)					
		.5	Association between doses, daytime treatment regimen and fatigue evolution (every three months)					

CT24-GSOP-SD-GL04 NI Study SAP Template; Template Version 1.0, Effective 31-Dec-2013 Page 23 of 29

PFIZER CONFIDENTIAL

	.6	Association between temporary daytime interruptions and fatigue evolution (every three months)
	3	Data from the patient diary
	.1	Daytime rest (weekly)
	.2	Physical exercise (weekly)
	.3	Has taken the medication (weekly)
•-	4	Quality of life (FACIT_Fatigue) (every six weeks)
	.1	Association between daytime habit and evolution on the Facit_Fatigue (every six weeks)
	.2	Association between daytime physical exercise and evolution on the Facit_Fatigue (every six weeks)
	.3	Association between daytime medication-taking habits and evolution on the Facit_Fatigue (every six weeks)

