	.4	Association between daytime dose changes and evolution on the Facit_Fatigue (every six weeks)
	.5	Association between doses, daytime treatment regimen and evolution on the Facit_Fatigue (every six weeks)
	.6	Association between temporary daytime interruptions and evolution on the Facit_Fatigue (every six weeks)
.4	5	Treatment, dose changes and temporary interruptions
· ·	7	Efficacy analysis
	.1	Number of treatment cycles received
	.2	Best response rate achieved with first-line treatment
	.3	ORR, DOR
	.4	Time on treatment and time to best response
	.5	Time to Treatment Failure (TTF)
	.6	Progression-free survival (PFS)
	.7	Reason for termination of treatment and reason for death

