#### Functional Assessment of Chronic Illness Therapy (FAC1T) Fatigue Scale (Version 4)

Below is a list of statements that other people with your illness have said are important. Please circle or mark one number per line to indicate your response as it applies to the past 7 days

		Not at all	A little bit	Somewhat	Quite a bit	Very much
1	I feel fatigued	0	1	2	3	4
2	I feel weak all over	0	1	2	3	4
3	I feel listless ("washed out")	0	1	2	3	4
4	I feel tired	0	1	2	3	4
5	I have trouble starting things because I am tired	0	1	2	3	4
6	I have trouble finishing things because I am tired	0	1	2	3	4
7	I have energy	0	1	2	3	4
8	I am able to do my usual activities	0	1	2	3	4
9	I need to sleep during the day	0	1	2	3	4
10	I am too tired to eat	0	1	2	3	4
11	I need help doing my usual activities	0	1	2	3	4
12	I am frustrated by being too tired to do the things I want to do	0	1	2	3	4
13	I have to limit my social activity because I am tired	0	1	2	3	4

Scoring: Items are scored as follows: 4=Not At all. 3=A Little bit; 2=Somewhat; l=Quite A Bit; 0=Very Much, EXCEPT items #7 and #8 which are reversed scored. Score range 0-52. A score of less than 30 indicates severe fatigue. The higher the score, the better the quality of life.

Item Number	Reverse Item?		Item Response	Item Score
1	4	-		=
2	4	-		=
3	4	-		=
4	4	-		=
5	4	-		=
6	4	-		=
7	0	+		=
8	0	+		=
9	4	-		=
10	4	-		=
11	4	-		=
12	4	-		=
13	4	-		=

Sum individual item scores: \_\_\_\_\_

Multiply by 13:

Divide by number of items answered:

For guidelines on handling missing data and scoring options, please refer to the Administration and Scoring Guidelines on-line at www.facit.org.

Source: Webster, K, Celia, D, & Yost, K. (2003). The functional assessment of chronic illness therapy (FACIT) measurement system: properties, applications and interpretation. *Health and Quality of Life Outcomes*, 1(79), 1-7.

Reprinted with permission from: http://www.facit.org/FACITOrg/Questionnaires

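### On the nominal schedule, six-weekly home FACIT-Fatigue forms recall the break on sunitinib 4/2 and 2/1 but on-drug days on continuous TKIs, and no planned analysis is aligned to the recall week

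*Protocol*

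**What the plan says.** Protocol 7.1 and SAP 2.1 ask the patient to fill in FACIT-Fatigue at home "at the start of each cycle", and define the pazopanib and sorafenib cycle as six weeks. The questionnaire asks patients to "indicate your response as it applies to the past 7 days" (SAP Annex 1). SAP 8.2.3 evaluates change at "week 6, week 12, week 18, week 24, week 30 and week 36", and Table 3.4 is listed as "Quality of life (FACIT_Fatigue) (every six weeks".

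The regimens listed in SAP 8.2.2 are sunitinib 4/2, sunitinib 2/1, and continuous pazopanib and sorafenib. Protocol 5 says that fatigue on sunitinib "increases in intensity during weeks 3 and 4, and tends to improve during the 2-week off-treatment period", when patients feel better than in the weeks on drug.

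The planned summaries are the mean and other descriptive statistics, the share of patients scoring below 30, and a change category (more than 4 points up, within 4 points, more than 4 points down) against the previous form. In addition, "comparisons of paired data will be performed for each one of the assessments with regard to the baseline value" and to the previous one. Table 3.4.5 is "Association between doses, daytime treatment regimen and evolution on the Facit_Fatigue (every six weeks".

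FACIT-Fatigue is also due at clinic visits at months 3, 6 and 9 (Protocol 7.1 and 7.2). It may be given at additional visits, for which Protocol 7.1 offers day 15 as an example.

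**The concern.** Where a form falls in the cycle decides whether its 7-day recall describes days on drug or days off drug. The six-weekly grid lands at the end of the scheduled break on both sunitinib schedules. On the continuous drugs there is no break.

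The protocol's own background treats phase as relevant to 4/2 fatigue. A pooled FACIT-Fatigue mean would then combine two different states without saying so. A reader who takes it as fatigue while on drug would get too favourable a picture of 4/2: a higher mean, fewer scores below 30 and a smaller decline from the untreated baseline. At week 6 the previous form is also the untreated one, so an association between regimen and change category would carry the difference in phase as well as any difference between regimens.

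**Working it through.** **Inputs.** Form timing: Protocol 7.1, SAP 2.1. Recall of 7 days: SAP Annex 1. Evaluation weeks: SAP 8.2.3. Sunitinib 4/2 is 28 days on and 14 off; 2/1 is 14 on and 7 off (Protocol 5). Pazopanib and sorafenib are continuous (SAP 8.2.2). Assumptions for the nominal case: day 1 is the first dose, the form is completed on day 1 of the new cycle and recalls the 7 days before it, and no cycle is delayed.

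**Step 1, the grid.** Six-week steps, 6 × k for k = 1 to 6, give weeks 6, 12, 18, 24, 30 and 36, which reproduces the SAP list. The form for week w falls on day 7w + 1, that is days 43, 85, 127, 169, 211 and 253. The recall is days 7w − 6 to 7w.

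**Step 2, phase.** Every 7w on the grid is a multiple of 42 and of 21, so the recall is always the last week of a cycle.
- 4/2: cycle days 36–42; the break is days 29–42; 0 of 7 days on drug at all six points.
- 2/1: cycle days 15–21; the break is days 15–21; 0 of 7 at all six points. Reading the 2/1 cycle as three or six weeks makes no difference.
- Continuous: 7 of 7 at all six points.

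Both sunitinib schedules are on drug for 28/42 = 14/21 = 67% of the time.

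**Step 3, departures from the nominal case.** A form completed k days late holds k on-drug days (k = 1 to 7) on either schedule, all from the first week of the new cycle. If the weeks are fixed by calendar and the cycles have slipped by s days, 4/2 stays at 0 up to s = 7 and reaches 7 at s = 14, while 2/1 reaches 7 at s = 7. The documents give no completion window and do not say whether weeks are counted by cycle or by calendar.

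**Step 4, clinic forms.** There are two readings of months 3, 6 and 9.
- As weeks 12, 24 and 36: clinic and home forms coincide, and the recall is again 0 of 7.
- As calendar months of 30.44 days: forms on days 92, 184 and 275. On-drug days are 7, 7, 7 on 4/2 and 7, 6, 1 on 2/1. On 4/2, only 0, 1 and 7 of these lie in weeks 3–4 (cycle days 15–28).

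**Step 5, what a phase difference would do on 4/2.** Let D be the points by which a patient's end-of-break score exceeds the on-drug score. The documents do not give D. If the on-drug fall from baseline is c, the week 6 form records c − D, so worsening is recorded only if c > 4 + D. An on-drug score x is counted as severe only if x + D < 30. For assumed D = 2, 4, 6:
- on-drug falls of 5–6, 5–8 and 5–10 points are recorded as maintenance;
- on-drug scores of 28–29, 26–29 and 24–29 are counted as not severe.

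These are illustrations, not estimates.

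**Step 6, planned analyses.** SAP 8.2.3 and Tables 3.4.3 to 3.4.6 relate FACIT change over six weeks to medication-taking, dose changes, regimen and interruptions. The weekly diary has an answer for taking no medication that week (tabulated in Table 3.3.3), and SAP 8.2.3 also describes a most-frequent-answer summary over 12 weeks. On either nominal sunitinib schedule only 4 of 12 weeks are off, so such a summary tends to hide them. None of these analyses matches the diary week to the week the form recalls.

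**The case against.** The strongest reply is that a start-of-cycle form is a consistent anchor in a descriptive, non-interventional study, and that the primary objective names no phase. This stands in part. If home forms supply every point and cycles run to plan, changes against the previous form from week 12 on compare like with like. The pooled level, the share below 30, the change from baseline and the week 6 association are not protected in that way.

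On-drug observation is also possible within the plan. A day 15 form would recall days 8–14, on drug under both schedules, and CTCAE fatigue is graded at months 3, 6 and 9. But the additional visits are optional, and the CTCAE grade is not the primary measure.

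Four stronger readings are tempting but not supported.
- A reader might infer that the SAP never relates FACIT to drug-taking. It does, in Table 3.4.3 and related analyses; what is missing is alignment to the recall week.
- A reader might infer that clinic forms at weeks 12, 24 and 36 make every later change on 4/2 switch phase. That needs calendar months. The SAP pairs three months with 12 weeks in its diary summary, and on that reading the switching disappears.
- A reader might infer a pooled shift comparable with the SAP's 4-point rule. The documents give neither D nor the sunitinib share, an all-on-drug mean is not the stated target, and the 4-point rule classifies one patient's change, not a group mean.
- A reader might extend the effect to 2/1. Protocol 5 describes the easing for the two-week break only.

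On objective 4, the list in Protocol 7.1 is illustrative, so its silence on off-treatment periods proves little. The omissions from Protocol 7.7 and SAP 2.2 remain.

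**Conclusion.** The concern holds as a matter of sampling and labelling. On the nominal schedule, all six home forms recall 0 of 7 on-drug days on sunitinib 4/2 and 2/1, against 7 of 7 on continuous drugs. By the protocol's own account of 4/2, pooled results would tend to understate on-drug fatigue on that schedule. At week 6, regimen and phase cannot be separated on nominal home forms.

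This rests on day 1 completion and undelayed cycles; late forms or slipped cycles make the phase vary unrecorded. The size in FACIT points is unknown, and an effect on 2/1 is an assumption. Whether clinic forms differ in phase from home forms depends on whether months 3, 6 and 9 are calendar months, which the SAP does not settle. It should be fixed before analysis.

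**What to change.** In SAP 8.2.3 and Table 3.4:

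1. Flag each FACIT form as on, off or mixed/unknown from regimen, cycle timing and the diary entry for the recall week, as far as the case report form allows.
2. Report the mean, the share below 30 and the change from baseline by regimen (4/2, 2/1, continuous) and by flag beside the pooled result. Label start-of-cycle sunitinib scores as end-of-break fatigue.
3. Present the week 6 regimen association with the caveat that regimen and phase are confounded on nominal home forms.
4. State whether home or clinic forms supply weeks 12, 24 and 36, and whether weeks are counted by cycle or by calendar. Do not mix home and clinic forms in one series of changes against the previous form without the flag.
5. Use clinic, additional-visit (such as day 15) or late forms for a within-patient on/off contrast where they exist. Nominal home forms alone cannot give one, because there the flag merely separates sunitinib from the continuous drugs.
6. Reconcile off-treatment periods, named in protocol objective 4, with Protocol 7.7 and SAP objective 4, which leave them out.

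The cost is one derived variable, extra table rows, smaller subgroups and some forms of unknown phase. The diary is weekly, and the SAP variable list gives interruptions as counts per cycle, so an exact day count may not be possible. No dose or schedule change is involved.
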